#### 5.4.2 BCC Lesion Exclusion Criteria

- 1. Recurrent or previously treated lesions
- 2. Lesions within 1 cm of the eyelids or lips, or on the hands, feet, ears, nose, and genitalia
- 3. Histological evidence of any other tumor in the biopsy specimen
- 4. Histological evidence of infiltrative, desmoplastic, sclerosing, or morpheaform BCC subtypes in the biopsy specimen
- 5. Medium- and high-risk basal cell carcinomas as defined by the National Comprehensive Cancer Network (NCCN) or Mohs Appropriate Use Criteria (i.e., BCCs eligible for Mohs surgery).

### TARGET LESION EXCLUSION ONLY:

- 6. For subjects with severe stasis dermatitis, target BCC lesions may not be on the lower extremities
- 7. Within 2 cm of the target BCC lesion(s):
  - a. Treatment with the following topical agents within the 12 weeks prior to the screening visit: aminolevulinic acid, 5-fluorouracil, corticosteroids, diclofenac, imiquimod, ingenol mebutate
  - b. Treatment with surgical excision, or curettage within the 2 weeks prior to the screening visit
  - c. Evidence of dermatological disease or confounding skin condition that may interfere with clinical evaluation (i.e., psoriasis, atopic dermatitis, eczema, propensity to form keloids or hypertrophic scarring)
  - d. Use of topical immunomodulators during study
- 8. Within 5 cm of the target BCC lesion(s): history of any skin cancer, except for other currently identified target and nontarget BCC lesions
- 9. Target BCC lesion is in the area of prior resurfacing procedure with CO2 laser or any photodynamic and phototherapy treatment within the 3 months prior to the screening visit.

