## 5.4 BCC Lesion Eligibility

Eligible lesions are those that meet the BCC lesion eligibility specifications described herein, from samples that are either from:

- *HISTORICAL* punch or shave biopsies (i.e., samples collected according to clinical standard of care collected within the 90 days prior to W1D1);
- A 2-mm punch biopsy collected within 90 days of W1D1 for suspected BCC ≥0.5 cm to 1.0 cm, and 3-mm punch biopsy for suspected BCC >1.0 cm to 2.0 cm; or
- A shave biopsy performed according to standard of care to include superficial or middle papillary dermis collected within 90 days of W1D1.

Lesions must meet the following criteria to be eligible for treatment with VP-315 as target lesions or for observation as nontarget lesions. Up to 2 target lesions may be treated, and any eligible lesions that do not receive treatment (up to 3) will be tracked as nontarget lesions for abscopal effect.

Lesions that meet the inclusion criteria and are only excluded by Criteria 6 through 9 in Section 5.4.2 below (TARGET LESION EXCLUSION) may be tracked as nontarget lesions. Lesions that do not meet the inclusion criteria or are excluded by BCC Lesion Exclusion Criteria 1 through 5 below will not be treated or observed (i.e., ineligible) and should be excised after completion of the study unless otherwise clinically indicated.

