### 7.3. Demographics and Baseline Characteristics

A summary of Demographics and Baseline Characteristics will be provided for enrolled subjects and for the analysis populations listed in Section 6 of this SAP. Baseline values will be used in summaries of parameters collected at multiple visits.

Descriptive statistics will be provided for the following parameters:

- Age (years),
- Height (cm),
- Weight (kg),
- Body Mass Index (BMI) (kg/m^2),
- Serum Tryptase (ug/L),
- Total Number of Clinically Diagnosed BCC Lesions where a Clinically Diagnosed BCC Lesion means any reported lesion with a non-missing date of clinical diagnosis of BCC,
- Total Number of Pathology Diagnosed BCC Lesions where a Pathology Diagnosed BCC Lesion means any reported lesion with a non-missing date of dermatopathology diagnosis of BCC,
- Smallest Lesion Diameter Before Biopsy (cm),
- Largest Lesion Diameter Before Biopsy (cm), and
- Duration of Disease (months) where Duration of Disease = (Treatment Start Date – Earliest Date of Dermatopathology Diagnosis of BCC) / 30.4375.

The number and percentage of subjects will be provided for the following parameters:

- Sex (Male, Female),
- Female Childbearing Potential (Yes, No),
- Race (American Indian or Alaska Native, Asian, Black or African American, Native Hawaiian or Other Pacific Islander, White, Mixed Race, Unknown or Not Reported),
- Ethnicity (Hispanic, Not Hispanic, Unknown or Not Reported),
- Fitzpatrick Skin Type (I-VI),
- Histologic Diagnosis at Screening (Micronodular, Nodular, Superficial) for TL1, TL2, NTL1, NTL2, NTL3, and

- BCC Location at Screening (Face or Neck, Clavicle or Shoulder, Arm, Chest or Abdomen, Back, Buttocks or Groin, Leg or Foot) for TL1, TL2, NTL1, NTL2, NTL3.

Separate listings using enrolled subjects will be provided for the following:

- Demographics and Baseline Characteristics (Age, Sex, Female Childbearing Potential, Race, Ethnicity, Height, Weight, BMI, Fitzpatrick Skin Type, Duration of Disease),
- Screening Clinical Evaluation (Lesion Number, Lesion Diameter (cm), Location, Date of Clinical Diagnosis, Date of Dermatopathology Diagnosis, Histologic Diagnosis),
- Screening Biopsy (Lesion Number, Biopsy Performed (Yes, No), Visit, Biopsy Date, Timing of Biopsy (Historical, At screening), Biopsy Type (Punch, Shave), Size of Punch Biopsy (2mm, 3mm, Other), Biopsy Sutures Removed (Yes, No), Date Biopsy Sutures Removed), and

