### **8.4. Abscopal Effect Based on Non-treated Lesions at Excision**

An abscopal effect is a phenomenon whereby the treatment of target lesions leads to improvement in both treated and non-treated lesions.

A summary of (a) histologic clearance and (b) clinical clearance for non-treated lesions will be provided to investigate a possible abscopal effect using EOT data and the full analysis population.

The histologic clearance will follow Section 8.1 of this SAP except for using the histologic diagnosis of excised non-treated lesions (NTL1, NTL2, NTL3), and the clinical clearance will follow Section 8.2 of this SAP except for using the PGA of non-treated lesions (NTL1, NTL2, NTL3). The summary will be provided by clearance (Histologic, Clinical) within lesion (NTL1, NTL2, NTL3). The summary will also be run using the per-protocol population as outlined in Section 6 of this SAP.

A separate listing will be provided for the excision of all lesions as described in Section 8.1 of this SAP, and a separate listing will be provided for the PGA of all lesions as described in Section 8.2 of this SAP.

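### SAP 8.4 tabulates clearance of nontarget lesions as possible abscopal effect without regard to how near they lie to an injected lesion, and the protocol sets no minimum distance

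*Protocol*

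**What the plan says.** **Eligibility.** Protocol 5.4 states that "any eligible lesions that do not receive treatment (up to 3) will be tracked as nontarget lesions for abscopal effect". The target-only exclusions do not keep a lesion out of this group: otherwise qualifying ones that "are only excluded by Criteria 6 through 9 in Section 5.4.2 below (TARGET LESION EXCLUSION) may be tracked as nontarget lesions". A nontarget lesion must therefore meet the inclusion criteria and avoid exclusions 1 to 5 only. The one location rule among those five is anatomical: "Lesions within 1 cm of the eyelids or lips, or on the hands, feet, ears, nose, and genitalia".

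Criterion 8, which applies to target lesions only, covers a 5 cm zone around the target. It excludes a "history of any skin cancer, except for other currently identified target and nontarget BCC lesions".

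**Analysis.** SAP 8.4 describes an abscopal effect as one in which "treatment of target lesions leads to improvement in both treated and non-treated lesions". It then plans the output: "A summary of (a) histologic clearance and (b) clinical clearance for non-treated lesions will be provided to investigate a possible abscopal effect". On layout it says: "The summary will be provided by clearance (Histologic, Clinical) within lesion (NTL1, NTL2, NTL3". SAP 8.3 also summarises remaining tumor volume, and its reduction, for NTL1 to NTL3. SAP 5.5 limits summaries to study part and cohort and rules out further subgroups.

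**Location data.** SAP 7.3 summarises, for each of the five lesion slots, "BCC Location at Screening (Face or Neck, Clavicle or Shoulder, Arm, Chest or Abdomen, Back, Buttocks or Groin, Leg or Foot". SAP 8.4 also calls for the excision listing of SAP 8.1, which shows location and histologic diagnosis for every lesion.

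**The concern.** An abscopal effect is of interest because the untreated lesion lay beyond direct reach of the drug and of the reaction at the injected site. The eligibility rules do not secure that. A nontarget lesion may adjoin an injected lesion and still be followed for abscopal effect.

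If such a lesion clears, two explanations compete: a distant immune response, or local spread of drug or inflammation. The planned table shows both in the same row. Abscopal effect is a listed secondary endpoint in Part 2, and Cohorts 4 and 5 are meant to inform a pivotal design. What is at stake is whether a clearance in that table can be cited as evidence of a distant effect.

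**Working it through.** The plan gives no abscopal rate, power or sample-size figure on this point, so there is nothing to reproduce. The check is a reading of the rules followed by a geometric illustration.

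**Step 1. Is separation required anywhere?**

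- Protocol 5.4.1 (inclusion) concerns size, histology and biopsy timing. It says nothing about distance from a target.
- Protocol 5.4.2, exclusions 1 to 5, concern prior treatment, anatomical site, other tumor, histologic subtype and risk class. None refers to the injected lesion.
- Protocol 5.4.2, exclusions 6 to 9, do not restrict nontarget lesions. Criterion 8 also exempts them by name from the 5 cm zone around a target.

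No minimum distance is set.

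**Step 2. Does the analysis make up for it?** The SAP 8.4 summary is arranged by type of clearance within lesion number, and by part and cohort. Neither body region nor distance enters. SAP 5.5 rules out adding a near/far split without an amendment.

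**Step 3. Is direct reach physically plausible?** Inputs from the documents:

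- The targeted volume is 500 µL (0.5 mL) per treatment day (Protocol 7.3).
- Lesion diameter is 0.5 to 2 cm (Protocol 7.3).

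The assumption, not in the documents, is that one dose spreads as a flat disc of thickness *t* = 1 to 4 mm, centred on the lesion.

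Radius: r = √(0.5 / (π × t)), with t in cm. Reach past the lesion edge: r − d/2, where d is the lesion diameter.

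| t (cm) | r (cm) | d = 0.5 cm | d = 1.0 cm | d = 2.0 cm |
|---|---|---|---|---|
| 0.1 | 1.26 | 1.01 | 0.76 | 0.26 |
| 0.2 | 0.89 | 0.64 | 0.39 | −0.11 |
| 0.3 | 0.73 | 0.48 | 0.23 | −0.27 |
| 0.4 | 0.63 | 0.38 | 0.13 | −0.37 |

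Example: √(0.5 / (π × 0.1)) = 1.26 cm, and 1.26 − 0.25 = 1.01 cm. A negative value means that the disc stays inside the lesion.

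Direct contact is therefore possible around small targets, over a short distance, and unlikely around the largest. The model leaves out two features that could extend the reach: the second portion is injected at the lesion edges, and doses are repeated on 2 or 3 days per lesion in Cohorts 4 and 5. The documents give no basis for quantifying how far local inflammation spreads.

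**The case against.** The strongest reply is that the plan is modest and already holds much of the information.

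- **Descriptive and hedged.** SAP 8.4 speaks of a possible effect. There is no inference and no rule for declaring an abscopal response. The endpoint is exploratory in Part 1 and one of several secondary endpoints in Part 2. This stands, and it limits the severity. It does not remove the point, because a descriptive table is interpreted through its layout.
- **Location is not ignored.** The excision listing that 8.4 calls for shows location for target and nontarget lesions, so a reader can compare them subject by subject. This stands. The gap is in the summary table and in the absence of a distance.
- **Local reaction at nontarget lesions is recorded.** The Cutaneous Reaction Assessment grades each nontarget lesion (Protocol Appendix 1; SAP 9.5), and the lesions are photographed (Protocol 8.5.2). This stands, but SAP 8.4 does not link either to clearance.
- **Body region is a poor measure of proximity.** Two distant lesions on the back would share a category, while neighbours on shoulder and back would not. This stands, and it is why the split should supplement the planned summary and not replace it.

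A reader might also infer that the SAP pools all nontarget lesions into one abscopal rate. It does not: results are shown separately for NTL1, NTL2 and NTL3. Nor do the 2 cm and 5 cm zones in Protocol 5.4.2 define how far the drug acts. They concern prior treatments, confounding skin conditions and skin-cancer history.

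**Conclusion.** The point holds in a limited form. The criteria permit a nontarget lesion next to an injected one. The SAP 8.4 summary presents clearance without regard to location, so it cannot distinguish a local from a distant effect.

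The size of any bias cannot be estimated. The documents do not show how many nontarget lesions were close to a target, or how many cleared. A reader might try to infer a figure: if 20 to 40% were close and 30 to 50% of those cleared locally, the inflation would be 0.2 × 0.3 = 6 to 0.4 × 0.5 = 20 percentage points. Neither input has any source in the documents, and no pooled rate exists for it to apply to, so that range should not be used.

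The geometry shows only that direct reach is plausible around small lesions: about 0.4 to 1.0 cm past the edge of a 0.5 cm lesion, and at most 0.26 cm past a 2 cm lesion. It rests on one dose, a centred flat disc and an assumed thickness.

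This is a cheap improvement to how a secondary endpoint can be read. It does not affect the primary safety objectives.

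**What to change.** In SAP 8.4, and for the NTL rows of SAP 8.3:

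1. Keep the planned summary unchanged.
2. Add a supplementary descriptive split of nontarget lesions by whether they share a body-location category (SAP 7.3) with any treated lesion of the same subject. Show it for Part 2 overall only, because a split by cohort would leave sparse cells.
3. Amend SAP 5.5 to allow this one split.
4. Footnote same-region clearances as 'local effect not excluded', and base any abscopal statement mainly on different-region lesions.
5. For each cleared nontarget lesion, list the treated lesion's location, the nontarget lesion's Cutaneous Reaction Assessment findings and, where existing photographs allow, the distance to the nearest treated lesion.

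The cost is SAP wording, one extra table and a fuller listing, all from data already collected. Measuring distance from photographs takes some effort and may not be possible for every lesion. The change should be made before database lock, since SAP 5.2 treats later additions as post hoc.

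The downside is fewer lesions in the abscopal row, and a coarse proxy that will misclassify some lesions in both directions. The listed distance and reaction findings partly offset this.

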### 6. SUBJECT ENROLLMENT

It is the responsibility of the investigator to ensure that subjects are eligible to participate in the study prior to enrollment and throughout the study.

Approximately 80 adult subjects ≥18 years of age will be enrolled into the study.

Before subjects begin participation in any study-specific activities/procedures, the Sponsor requires a copy of the site's written Institutional Review Board (IRB) approval of the protocol, ICF, and all other subject information and/or recruitment material, if applicable. All subjects and/or legally acceptable representatives must personally sign and date the ICF before commencement of study-specific activities/procedures.

When the investigator determines that the subject meets all of the inclusion criteria (Section 5.2) and none of the exclusion criteria (Section 5.3), confirmation of eligibility and the date of confirmation is recorded in the subject's medical record and in/on the enrollment electronic case report form (eCRF).

Each subject who enters into the screening period for the study (defined as the point at which the subject provides written informed consent) receives a unique identification number before any study procedures are performed.

Subjects who meet the eligibility requirements for entry into this open-label study (Section 5.2 and Section 5.3) will be sequentially enrolled, with each subject receiving the next available subject number (beginning with 001). Enrolled subjects will receive study drug on Day 1 in accordance with the study treatments described in Section 4.1 (Figure 7-2).

#### 7. TREATMENT AND TREATMENT PROCEDURES

## 7.1 Randomization and Blinding

This is an open-label, multicenter, dose-escalating study. Eligible subjects will be enrolled sequentially.

VP-315 will be dispensed by the study pharmacist, or designee, in an open-label fashion to the subjects. All Screening tests and procedures must be completed prior to the administration of the first dose of study drug on Day 1. Once a subject number has been assigned to a subject, it will not be reassigned to another subject. Replacement subjects may be enrolled if subjects do not complete all EOT lesion excisions. Replacement subjects will not be enrolled for subjects who discontinue the study due to treatment-related toxicity, including subjects who have not completed all lesion excisions. A new unique subject number will be assigned to the replacement subject.

## 7.2 Description and Handling

#### 7.2.1 Formulation

LTX-315 is an oncolytic peptide provided as LTX-315 Acetate 20 mg/vial lyophilized powder for injection that will be reconstituted in saline to a concentration ranging from 4 to 20 mg/mL based upon the target dose and volume for each subject. The single excipient, water for injection (WFI), is of pharmacopeial quality; the WFI is removed by lyophilization. LTX-315 is supplied in colorless glass vials (Ph. Eur. hydrolytic class I) fitted with a rubber stopper (Ph. Eur. type I).

### 7.2.2 Storage and Handling

Unreconstituted LTX-315 vials (20 mg/vial) must be stored as follows:

- refrigerated at 2-8°C (36- 46°F) or
- frozen at  $-20 \pm 5$  °C (-13° to 5°F)
- protected from light at the study site, separated from other drugs.

The reconstituted LTX-315 solution can be stored for up to 12 hours in a refrigerator at 2-8°C (36–46°F). Syringes with LTX-315 drawn from the vial can be stored for up to 4 hours at 20-25°C (68-77°F) protected from light. Any unused portion should be discarded.

Storage conditions for LTX-315 are specified on the label. All vials of investigational product should be stored in a securely locked area, accessible only to authorized site personnel until reconstitution. To ensure the stability and proper identification, investigational product should not be stored in a container other than the containers in which they were supplied.

Additional information regarding storage, handling and reconstitution is provided in the Pharmacy Manual.

### 7.3 Dosage, Administration, and Schedule

VP-315 will be administered via intradermal injection into a single target lesion (between  $\geq$ 0.5 cm and  $\leq$ 2 cm in longest diameter) using the 1-mL syringe and 30-gauge ½-inch needle provided by Verrica. The subjects should be positioned in a way so that the target lesion lies flat, to avoid any dependent areas that may be susceptible to leakage of VP-315. Subsequent injections for the same lesion will be given in remaining nonnecrotic areas of the lesion, as assessed prior to treatment. In Parts 1 and Part 2 (Cohorts 4 and 5), each 500-μL dose will be divided into 2 injections given at least 15 minutes and no more than 30 minutes apart, with 30% (150 μL) administered in the first injection and the remaining 70% (350 μL) with the second injection. In all parts of the study, the targeted total volume of delivery is 500 μL daily.

In Part 2, refer to Table 7-1 for cohort dosing and regimen.

For all injections, VP-315 is injected intradermally. It is critical to assure adequate and even distribution of VP-315 across the entire base of the lesion. To accomplish this, the first 150 µL is to be injected as centrally as possible such that the VP-315 can distribute radially outward. The second (350-µL) portion shall be injected in a clockface fashion (i.e., 12, 3, 6, 9 o'clock [shown below in Figure 7-1]) as needed to ensure uniform distribution, into the edges of the lesion to infiltrate the entire tumor with VP-315. Insert the needle at a 10- to 20-degree angle for a flat lesion, or at an increased angle for a raised lesion. Subcutaneous injection should be avoided.

9 C 3

Figure 7-1
Injection Pattern for VP-315

The maximum total daily dose of VP-315 in any treatment visit in any subject or cohort must not exceed 8 mg.

# 7.3.1 Management of Postinjection Reactions to VP-315

Should a subject experience a post-injection reaction to VP-315 administration, the investigator should treat the subject in accordance with institutional guidelines.

In Part 1, for any Grade 1 (per CTCAE V5) postinjection reaction (with the exception of local reactogenicity) occurring during VP-315 injections, or within 1 hour after the last injection, injections should stop until resolution of the reaction. If the reaction occurs during the first injection of the dose and resolves within 1 hour, the second injection of the dose may continue.

For Grade 2 and higher reactions, the investigator must stop further injections in accordance with TRAE SI/DLT descriptions (Section 10.2).

In Part 2, subjects will continue to be closely monitored for any safety signaling. If a TRAE SI is identified (Section 10.2), the medical monitor will review and determine if treatment should be continued.

# 7.3.2 VP-315 Dosing Strategy

## **7.3.2.1** Study Part 1

In Part 1 of the study, the starting total daily dose for the evaluation of VP-315 will be 2 mg for the first subject. Subjects will receive ascending once-daily doses (increasing in 1-mg increments for up to 3 days in a 7-day treatment week [≥4 days off between treatment weeks]) until the first lesion is necrosed or until the subject experiences a DLT, whichever occurs first (Figure 7-2). Subjects will be observed for DLTs throughout the treatment period during Part 1.

After receiving a dose, the subject will return to the clinic the following day for assessment by the investigator. If, in the opinion of the SRC (see Section 7.4), there has been no DLT and if the lesion is not necrotic, the dose will be escalated, and the same lesion will continue to be treated before any additional target BCC lesions may be treated.

When a target lesion is deemed necrotic in the opinion of the SRC, the subject will not receive any additional treatment for that lesion, and a safety assessment visit will be performed instead. If the subject has additional lesions and no DLT has occurred, treatment of the next lesion may begin on day 1 (D1) of the next week. A maximum of 2 target BCC lesions may be treated, and only 1 lesion may be treated at a time. Subjects will be treated for a maximum of 2 weeks and a maximum total daily dose of 8 mg.

The starting dose will be escalated between subject cohorts in 1-mg increments after the previous cohort has completed Week 1 dosing (the DLT observation period) (Table 7-1). Dose escalation in Part 1 will end when 2 subjects experience a DLT at the same nominal dose (indicating that the preliminary MTD has been exceeded, and the preliminary MTD is the dose immediately below where any DLT occurred) or until a maximum VP-315 total daily dose of 8 mg is reached in up to 6 subjects.

## 7.3.2.2 Study Part 2

Part 2 will be initiated upon completion of Part 1 to determine the optimal dosing regimen of VP-315. There were no DLTs observed in Part 1 of the study and the maximum dose of 8 mg was achieved. Therefore, the dose to be evaluated in Part 2 will be a total daily dose of 8 mg in the following 5 Cohorts:

- Cohort 1 (N=3-6): The planned dosing regimen in Week 1 of Part 2 will begin with a VP-315 loading dose on Week 1/Day 1 (W1D1) at half the target dose, followed by total daily doses at the full target dose for the remaining dosing days of the treatment week, until the lesion is necrosed. Additional weeks of treatment will not include a loading dose on W2D1. Subjects may be treated for a maximum of 2 weeks (W1D1, W1D2, W1D3 and W2D1, W2D2, W2D3 up to 6 total doses).
- Cohort 2 (N=3-6): VP-315 once-daily dosing of 8 mg on all treatment days (i.e., no loading dose on W1D1) up to 3 consecutive daily doses/week for up to 2 weeks (W1D1, W1D2, W1D3 and W2D1, W2D2, W2D3 up to 6 total doses).

The study design and dosing strategy listed below for Cohorts 3, 4 and 5 are recommendations from the Safety Review Committee following an adhoc safety review meeting held on June 13-14, 2023 to discuss subjects reports of pain and burning at the injection site that were not observed in Part 1 of the study:

• Recommendation: Remove/skip Cohort 3 in Part 2 of the protocol and advance from Cohort 2 to Cohorts 4 and 5. Revert to Part 1 dosing strategy of a 30/70 split dose for all treatments with the injections adminstered 15-minutes apart.

Cohort 3 (N=0): This cohort has been removed at the recommendation of the SRC.

For Part 2 (Cohorts 4 and 5) the highest total daily dose of VP-315 (8.0 mg) will be divided into a split dose; the first dose is not to exceed 2.4 mg (30% of 8-mg dose), and the remaining dose will not exceed 5.6 mg (70% of 8-mg dose) and administered 15 minutes apart (not to exceed 30 minutes).

- Cohort 4 (N= Appproximately 30 (10 initial/up to 20 expansion): (Two times weekly dosing) VP-315 once-daily dosing of 8 mg, administered 2 consecutive days in one week (W1D1, W1D2). The planned dosing regimen will be a split dose of VP-315 for all treatments. The 500μL (8 mg) dose will be divided into 2 injections given at least 15 minutes and no more than 30 minutes apart, with 30% (150 μL) administered in the first injection and the remaining 70% (350 μL) with the second injection. Treatment for a second target lesion may begin on D1 of the next week (W2D1, W2D2). Each individual target lesion is treated for the assigned 2 days only (regardless of necrosis status). Up to 2 target lesions may be treated up to 4 total doses.
- Cohort 5 (N= Approximately 30 (10 initial/up to 20 expansion): (Three times weekly dosing) VP-315 once-daily dosing of 8 mg, administered 3 consecutive days in one week (W1D1, W1D2, W1D3. The planned dosing regimen will be a split dose of VP-

315 for all treatments. The  $500\mu L$  (8 mg) dose will be divided into 2 injections given at least 15 minutes and no more than 30 minutes apart, with 30% (150  $\mu L$ ) administered in the first injection and the remaining 70% (350  $\mu L$ ) with the second injection. Treatment for a second target lesion may begin on D1 of the next week (W2D1, W2D2). Each individual target lesion is treated for the assigned 3 days only (regardless of necrosis status). Up to 2 target lesions may be treated – **up to 6 total doses.** 

After receiving a dose, the subject will return to the clinic the following day for assessment by the investigator. If, in the opinion of the Medical Monitor, the lesion is not necrotic Cohorts 1 and 2 only, the same lesion will continue to be treated before any additional target BCC lesions are treated. When a lesion is deemed necrotic in the opinion of the Medical Monitor, the subject will not receive any additional treatment for that lesion.

- If the subject has additional lesions, treatment of the next lesion may begin on D1 of the next week. A maximum of 2 target BCC lesions may be treated, and only 1 lesion may be treated at a time.
- Subjects in Cohorts 4 and 5 with only 1 target lesion that complete week one of treatment and the W1 safety assessment visit without complete necrosis should return for a Limited Safety Assessment Visit on W2D1 for further evaluation of the lesion for necrosis. No additional treatment will be provided.
- Subjects in Part 2 (all Cohorts) that complete week two of treatment and the W2 Safety Assessment Visit without complete necrosis should return for a Limited Safety Assessment visit on W3D1 for further evaluation of the lesion for necrosis. No additional treatment will be provided.

For the first 10 subjects enrolled into Cohorts 4 and 5: after each treatment, subjects will remain in the study center for up to 2 hours post second injection for safety monitoring (e.g., continuous blood pressure, electrocardiographic and AE monitoring).

Following the final treatment of the 10th subject in Cohort 4, enrollment into Cohort 5 may be initiated for 10 subjects.

